In our study, we will recruit female patients over the age of eighteen who have been previously scheduled to undergo a benign gynecological laparoscopic procedure. All patients consented will be eligible for same-day discharge.

Once consented, participants will be randomized into the pre-operative acupuncture (study) or sham acupuncture (control) group using a computer generated randomization system. There will be a total of 50 patients in each group. In the study group, the proposed acupuncture points are LR-3, GB-41, GB-34, TH-5, MH-6. These points are accepted in modern and traditional Chinese acupuncture as aiding in overall painful conditions and with reference to pelvic painful conditions. The PC-6 point is also widely accepted as a major point to reduce nausea and vomiting from any condition, and has been shown in operative and anesthesia literature as well with moderate evidence. Standard acupuncture needles 29 and 30 gauge will be used throughout. On average, it takes three minutes to place five to six acupuncture needles. Due to the rapid placement of the needles, subjects will not be under significantly more anesthesia than patients who do not participate in the study. All points are located on the patients upper and lower extremities and can be easily accessed in lithotomy position. In the study group, the needles will be left in-situ for a total of 15 minutes, as the patient is prepared for surgery. In the control group, the primary surgeon will place five superficial needles in specific predetermined locations on the

 Mount Sinai	Protocol Name:	The Role of Acupuncture in Post-Operative Pain Management in Gynecological Patients
	Principal Investigator:	[name]
	Primary Contact Name/Contact Info:	[name], [name]
	Date Revised:	6/19/2016
	Study Number:	1896888

patients' hands and feet. The points, chosen by the lead anesthesiologist, are outside the "meridian" acupuncture points. The needles in the control group will be placed only 1/8 centimeter deep and immediately removed. This poses no increased harm to the patient. Acupuncture needles can leave a very mild sensation over the skin. In order to completely blind the patient, needles must be placed in both groups. All needles will be removed before the first incision is made. All patients will be blinded to their group allocation.

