Inclusion criteria: Female patients over the age of 18 scheduled for laparoscopic gynecological procedures of the uterus, fallopian tubes, and/or adnexa benign disease will be included in our study.

Exclusion criteria: Males, women under 18 years of age, women who are pregnant or have suspected or known malignant disease, or women who are immunocompromised will be excluded from our study. Patients with known or persistent abuse of medication, drugs, or alcohol. Patients with chronic pain for greater than 3months will also be excluded.

 Mount Sinai	Protocol Name:	The Role of Acupuncture in Post-Operative Pain Management in Gynecological Patients
	Principal Investigator:	[name]
	Primary Contact Name/Contact Info:	[name], [name]
	Date Revised:	6/19/2016
	Study Number:	1896888

(NOTE: You may not include members of vulnerable populations as subjects in your research unless you indicate this in your inclusion criteria.)

c) Number of Subjects: 100

A total of 100 patients will be recruited and there will be 50 in the study group and 50 in the control group. This was determined because we are looking for a difference in narcotic use of 1.5 tablets to be considered significant. Assuming a standard deviation of 2.4 (prior data) , we will need to study 47 experimental subjects and 47 control subjects to be able to reject the null hypothesis that the population means of the experimental and control groups are equal and discern a difference of 1.5, with probability (power) 0.8. The Type I error probability associated with this test of this null hypothesis is 0.05.

d) Study Timelines

The anticipated duration of the study is 12 months including recruitment and data analysis. Eligible patients will be offered enrollment in the study during their pre-operative assessment with [name], [name], or [name] typically occurring 1-3 weeks prior to surgery. Patients will then be followed throughout their hospital course. Follow up will occur at their post-operative visits 2 weeks after the procedure.

e) Endpoints

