The purpose of the present study is to determine the effectiveness of acupuncture in post-operative pain management in laparoscopic gynecological procedures. The endpoints of this study are narcotic use at 24 hours, hospital admission for pain management, and narcotic use for 7 days following surgery. Primary outcome measures narcotic use at 24 hours. Secondary outcome measures are quantity of opioids used for pain management for the first 7 days post operatively and hospital admission.

Safety endpoints that would cause a subject’s participation to end are contact dermatitis from the placement of acupuncture needles. This is a very uncommon response.

f) Procedures Involved in the Human Research

Female subjects who are scheduled to undergo a laparoscopic surgery of the uterus, adnexa or ovaries for benign disease. All procedures will be performed for clinical patient care and not solely for research purposes. Patients will be offered enrollment in the study during their pre-operative visit with [name], [name], and [name] and consented by one of the participating fellows.

Once consented, participants will be randomized into the acupuncture (study) or sham acupuncture (control) group using a computer-generated randomization system. The patient will be blinded to the group to which they are assigned.

After general anesthesia induction and proper positioning of the patient, but prior to surgical incision, the acupuncture needles will be placed. In the study group, the proposed acupuncture points are LR-3, GB-41, GB-34, TH-5, MH-6, which are all found on upper and lower extremities. Standard

	Protocol Name:	The Role of Acupuncture in Post-Operative Pain Management in Gynecological Patients
	Principal Investigator:	[name]
	Primary Contact Name/Contact Info:	[name], [name]
	Date Revised:	6/19/2016
	Study Number:	1896888

acupuncture needles 29 and 30 gauge will be used throughout. As in standard acupuncture treatments, the needles will be left in-situ for a total of 15 minutes. In the control group, the primary surgeon (who has no acupuncture experience) will quickly place 5 needles in random spots on the patients' hands and feet. The needles will be immediately removed. Anesthesiologists will be informed to not make any alterations in their typical anesthesia regimen based due to the placement of acupuncture needles.

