Nursing staff will record the kind and dose of pain medications the patient requires in the PACU. This information will also be recorded on the data sheet. After four hours, [name] will determine if the patients will be discharged home or admitted. Reasons for admission include but are not limited to inadequate pain control, hemodynamic instability, conversion of laparoscopic case to laparotomy, or other adverse outcomes that necessitate close monitoring. Criteria for discharge include adequate pain control, hemodynamic stability, and patient ability to ambulate and tolerate oral intake. Assessment of pain medications used will occur at hours 24 and 48 hours postoperatively either in the hospital or over the phone if the patient was discharged. The patient will continue to keep track of her narcotic use until 10 days post-operatively. The patient will bring her data log of medications taken and her narcotic pill bottles with the remaining tablets to her post-operative visit.

The data will be analyzed and stored by the research team.

g) Specimen Banking

There will be no specimen banking

h) Data Management and Confidentiality

The data will be stored in password-protected spreadsheets in which the subject's identity will be de-identified with a unique coding system. The research data and linking codes will be filed separately. Data will be stored separately from unique identifiers that can link the data to a person's identity. All computer files will be stored on computers connected with the MSSM server, and will also be password protected and viewed only by the research team. Data will be stored indefinitely and will only be accessible by the co investigators. The data will include demographic information (the subject code, age, operation performed, study group) and outcome measure data including pain scale numbers, amount of pain medications taken, and quality of life survey answers.

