8. The points in question are safely accessible during positioning for gynecological procedures and do not impose an increased surgical or anesthetic risk. Treatment needles will be placed by a licensed acupuncturist. Control needles will be placed superficially in predetermined locations. These needles will only puncture the skin and then will be immediately removed.

9. The data will be collected and stored in an organized fashion and will be checked by multiple co investigators to ensure that it is complete and accurate.

10. If the patient is negative impacted in any manner, it will be reported to the IRB.

j) Withdrawal of Subjects

Subjects will be able to withdraw from the study at any time, except during the surgical procedure. It is not anticipated that subjects will be withdrawn from the study without their consent. If a

 Mount Sinai	Protocol Name:	The Role of Acupuncture in Post-Operative Pain Management in Gynecological Patients
	Principal Investigator:	[name]
	Primary Contact Name/Contact Info:	[name], [name]
	Date Revised:	6/19/2016
	Study Number:	1896888

subject chooses to withdraw early from the research the data collected up to that point of withdrawal will be analyzed using an intention to treat analysis

6) Risks to Subjects

Acupuncture will be given in a sterile fashion and the time it takes for a licensed acupuncturist to place the needles is less than 3 minutes. The needles in the control group will remain in place for fifteen minutes, at which time the patient will be prepped and draped in a normal sterile fashion. The needles in the control group will be placed superficially in the skin and immediately removed. The patient will not have an increased risk of infection or substantial time under anesthesia. Bleeding, cosmetic bruising, and infection are the present risks, but are extremely low and only reported as rare case reports. Pneumothorax has been quoted in the literature with thoracic points, however none of the points used will be in thoracic regions. Nerve damage is theoretical if in close proximity to a peripheral nerve but has not been reported. Foam pads will be placed around the hands and feet in order to prevent the movement of needles, even if external pressure is accidentally placed on the extremities. Lastly, all needles will be removed prior to start of the procedure.

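### The surgeon knows every patient's arm, and nothing in the plan keeps post-operative analgesic orders the same in both arms

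*Combined protocol and SAP*

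**What the plan says.** In the Combined protocol and SAP, the person who needles depends on the arm. For controls, Section 5(f) says "the primary surgeon (who has no acupuncture experience) will quickly place 5 needles" and the needles come out at once. For the study arm, Section 5(i) says "Treatment needles will be placed by a licensed acupuncturist", and Section 5(f) leaves those needles in for 15 minutes.

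On blinding, the opening summary says "All patients will be blinded to their group allocation", and Section 5(f) repeats this for the patient. No one else is said to be blinded.

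On co-treatment, the one instruction in Section 5(f) is "Anesthesiologists will be informed to not make any alterations in their typical anesthesia regimen based due to the placement of acupuncture needles".

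On post-operative analgesia, Section 5(f) says "Nursing staff will record the kind and dose of pain medications the patient requires in the PACU". It adds assessments of medication use at 24 and 48 hours, a patient log, and return of the pill bottles. No drug, strength, schedule, order set or dispensed quantity is fixed, and the prescriber is not identified.

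On timing, Section 5(f) says "Once consented, participants will be randomized into the acupuncture (study) or sham acupuncture (control) group using a computer-generated randomization system". Consent is taken at the pre-operative visit, 1-3 weeks before surgery.

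**The concern.** The surgeon either needles the patient or does not, so the arm is known in every case. The instruction to anesthesiologists shows that the authors saw how knowledge of the needling could change care, but the safeguard stops at the anesthesia regimen. The same risk applies to wound local anesthetic, PACU and inpatient orders, and the discharge prescription. All of these can affect how many tablets a patient takes in 24 hours.

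The bias could run either way:

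- **Hiding a benefit:** more non-opioid cover, or stronger tablets, for sham patients would lower their tablet count.
- **Creating an apparent benefit:** more non-opioid cover for acupuncture patients, or more frequent opioid dosing for sham patients, would widen the gap.

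Prescriber habits that do not depend on arm are balanced in expectation by randomization. Choices made because the arm is known are not, and recording them does not reliably allow the bias to be removed at analysis.

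This point is about co-treatment. The masking of outcome recorders and of the admission decision are separate matters.

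**Working it through.** **Does the surgeon know the arm?** Section 4, read alone, could suggest that the acupuncturist places all needles. The summary and Section 5(f) assign the sham needles to the surgeon, and Section 5(i) assigns the treatment needles to the acupuncturist. Section 6 has one sentence leaving control needles in for fifteen minutes, but the sentence after the next says they are removed at once, as the summary and 5(f) do. Whichever dwell time applies, the operator differs by arm, so the surgeon knows the assignment.

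**Does anything fix post-operative orders?** Section 5(f) records analgesics but does not standardize them. Its discharge criteria govern when a patient leaves, not what she is given. Nothing found elsewhere fills the gap.

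**Inputs for scale.** Section 5(c) plans on the basis that "we are looking for a difference in narcotic use of 1.5 tablets", with SD 2.4, power 0.8, Type I error 0.05 and 50 patients per arm. Section 5(h) gives a prior mean of 3 tablets. Sidedness is not stated, so I assume two-sided.

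**The plan's own figure.** The normal approximation gives n = 2 × [2.4 × (1.960 + 0.842) / 1.5]² ≈ 40.2, so 41 per arm; the t-based calculation gives 42. The stated 47 is not reproduced, but it errs on the safe side (t-test power about 0.85 at 47 and 0.87 at 50) and does not affect this point.

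**Effect of a net shift b (assumed).** Two-sample t-test, noncentral t, df = 98, SE = 2.4 × √(2/50) = 0.48. With no true effect, the noncentrality is b/0.48. With a true effect of 1.5 and a shift toward no difference, it is (1.5 − b)/0.48.

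| Net shift b (tablets) | Rejection probability, no true effect | Power, true effect 1.5 |
|---|---|---|
| 0 | 0.050 | 0.872 |
| 0.1 | 0.055 | 0.823 |
| 0.25 | 0.081 | 0.732 |
| 0.5 | 0.178 | 0.541 |

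**How many patients would have to be affected?** The number needed in one arm, all changed in the same direction, is 50 × b / (change per patient).

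| Net shift b | At 1.5 tablets each | At 1.0 tablet each |
|---|---|---|
| 0.1 | 3.3 | 5 |
| 0.25 | 8.3 | 12.5 |
| 0.5 | 16.7 | 25 |

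**Check with only some patients changed.** In simulations of 100,000 trials, I moved k sham patients by 1.5 tablets. With k = 8 (net 8 × 1.5 / 50 = 0.24), the false-positive rate was about 7.5% and power about 73%. With k = 17 (net 0.51), they were about 17% and 52%. The table is therefore not an artifact of assuming a uniform shift.

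**The case against.** The strongest reply is that the causal chain is incomplete. The documents do not say that the surgeon, or anyone else who knows the arm, writes the analgesic orders, or that anyone would vary them. The route is also narrow: "All patients consented will be eligible for same-day discharge", and a woman at home decides for herself, while blinded, how many tablets to take. Returned bottles mean that tablets dispensed are not assumed to be tablets taken. A 0.1-tablet shift does almost no harm, since power stays at 82%, above the planned 80%. The larger figures need about a third of one arm, all moved the same way by half the prior mean. Section 5(i) also plans a look at 50 patients, with stopping for a significant difference, so a single-test 5% baseline is not this trial's exact operating characteristic.

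Much of this stands. Exposure is limited, the shifts are assumptions, opposing changes would partly cancel, and the table is an illustration.

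It does not remove the gap. Patient blinding does not govern what she receives in the PACU or on the ward, or which drug and strength she is sent home with. Section 4 has surgeons, fellows and residents carrying out the study, so influence by a team that knows the arm is likely, though not stated. Recording drugs by kind and dose would let a difference be seen, but would not reliably allow it to be corrected.

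**Conclusion.** The concern holds. Followed as written, the plan lets the surgeon know every arm and leaves post-operative co-analgesia free to vary with it, on a route that feeds the 24-hour primary outcome. That bias will occur is not shown, and no intent to vary care is implied.

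The consequence ranges from negligible (0.1 tablet) to serious (0.5 tablet: about 18% false positives, or power of about 54%). This rests on SD 2.4, 50 per arm, one two-sided test at 0.05 and shifts that the documents do not supply. The change should be made because it is cheap beforehand and the bias cannot be reliably undone afterwards. Confidence is medium, because neither the prescriber nor the size of any shift is known.

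**What to change.** Amend Section 5(f) as follows.

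1. Extend the existing instruction to surgeons, fellows, residents and any other post-operative prescriber, and to wound local anesthetic.
2. Use one default post-operative and discharge analgesic order set in both arms (same drug, strength and schedule), with a stated default for wound local anesthetic, entered before surgery. Have someone who does not prescribe hold the assignment, for example in a sealed envelope. Release it to the surgical team only after induction, once the orders are in and needling is due.
3. Allow clinically needed departures, such as after conversion to laparotomy, and log each with its reason.
4. Add to the data sheet the wound local anesthetic used and the opioid drug, strength and quantity dispensed. Tabulate co-analgesia and order changes by arm.

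The cost is a protocol paragraph, a shared order set, a held assignment and a few data fields, with no extra visits or patients. Prescribers lose a little freedom, and the acupuncturist must be on hand before the arm is known.

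Wound local anesthetic and later order changes by someone who knows the arm would still be covered only by instruction and log. Having a non-prescriber place both needle sets out of the surgeon's view would close more of the route, but would change who performs the sham.

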SPSS will be used for the data analysis. A power analysis was performed using prior data of narcotic use in [name] post-operative gynecological patients. This data demonstrated the average number of narcotic tablets consumed at 24 hours is 3, with a standard deviation of 2.4. Overall we are aiming to achieve a decrease of 50% (or 1.5 tablets) for post-operative narcotic use at 24 hours. The number of patients required for such a difference is 47 experimental subjects and 47 control subjects. The Type I error probability associated with this test of this null hypothesis is 0.05. Further Data analysis will be performed using SPSS. The analysis of pain medication use and admission rate will be performed using student t-tests and regression analyses.

 Mount Sinai	Protocol Name:	The Role of Acupuncture in Post-Operative Pain Management in Gynecological Patients
	Principal Investigator:	[name]
	Primary Contact Name/Contact Info:	[name], [name]
	Date Revised:	6/19/2016
	Study Number:	1896888

i) Provisions to Monitor the Data to Ensure the Safety of Subjects

1. MSSM Principal Monitor: [name] (PI)

Academic Title: Director, Division of Gynecology

[contact]

Email: [contact]

2. The choice of principal monitor is appropriate to assess the risks to the participants because he is the lead attending in this study and the attending physician of all of the study participants. He has done a large amount of gynecology research and has ample experience in assessing the safety and well-being of the participants.

3. All adverse events including contact dermatitis will be assessed at the specified endpoints. In addition the efficacy of the acupuncture in reducing pain will be determined.

4. The data will be analyzed after 50 and 100 patients.

5. The study will be terminated if it is determined that there is a significant difference between the study groups in post-operative pain control or if there are multiple incidences of adverse events related to the study protocol.

6. In the past, there has been a very minimal risk of dermatitis with standard acupuncture needles.

7. Standard sterile acupuncture needles will be used.

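### The plan names Student t-tests, with unspecified regression, for the yes/no admission outcome; if admissions are rare, a t-based interval covers a true difference too seldom and tends to understate it

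*Combined protocol and SAP*

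**What the plan says.** Section 5(h), Data Management and Confidentiality, gives the only statement of method for this outcome: "The analysis of pain medication use and admission rate will be performed using student t-tests and regression analyses". It names two outcomes and two methods, does not pair them, and does not say what kind of regression is meant. No test for proportions, exact method or logistic model appears elsewhere.

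Section 5(e), Endpoints, makes admission a secondary outcome: "Secondary outcome measures are quantity of opioids used for pain management for the first 7 days post operatively and hospital admission". Section 5(f), Procedures, shows that it is binary: four hours after surgery a physician "will determine if the patients will be discharged home or admitted". Section 5(c) sets the size: "there will be 50 in the study group and 50 in the control group". No expected admission rate is given. The nearest statement, in the opening summary, is "All patients consented will be eligible for same-day discharge".

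**The concern.** A Student t-test compares means and takes its standard error from the sample variance. For a yes/no outcome that variance depends on the observed proportion and shrinks to zero as the count of admissions does. With few admissions, the standard error is smallest in exactly the samples that say least.

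Lowering the admission rate is part of the stated goal of the study, so the admission result will be read. At stake is whether its interval fairly shows what 100 patients can and cannot rule out.

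**Working it through.** **Inputs.** From the documents: 50 per arm, and alpha 0.05 ("The Type I error probability associated with this test of this null hypothesis is 0.05", stated for the primary test and carried over here). Two-sidedness is assumed, since the null in section 5(c) is one of equal means. Admission rates are assumed over a range. The plan has no figure for admission to reproduce; its sample size calculation concerns tablets at 24 hours.

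**The t interval on 0/1 data.** Let a and b be the observed proportions in the arms with the higher and lower true rate, and d = a − b. With n = 50 the pooled standard error reduces to SE = √{[a(1 − a) + b(1 − b)]/49}. The 95% interval is d ± 1.984 × SE (98 df).

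**The comparator.** Newcombe's interval uses the Wilson limits (l, u) of each arm. It runs from d − √[(a − l_a)² + (u_b − b)²] to d + √[(u_a − a)² + (b − l_b)²].

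**Coverage.** For each pair of true rates, all 51 × 51 possible results were weighted by their binomial probabilities. The table shows how often each interval contains the true difference, and on which side the t interval misses.

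| True rates | t coverage | t interval wholly below truth | t interval wholly above truth | Newcombe coverage |
|---|---|---|---|---|
| 2% v 1% | 77.3% | 22.5% | 0.2% | 99.9% |
| 4% v 2% | 86.4% | 13.1% | 0.5% | 99.2% |
| 4% v 1% | 86.7% | 13.0% | 0.2% | 99.6% |
| 5% v 2% | 91.5% | 8.1% | 0.5% | 98.9% |
| 8% v 2% | 90.8% | 8.5% | 0.7% | 97.8% |
| 10% v 2% | 93.5% | 5.5% | 1.0% | 97.5% |
| 10% v 5% | 94.7% | 3.6% | 1.7% | 96.9% |
| 15% v 5% | 94.3% | 3.7% | 1.9% | 96.0% |
| 20% v 10% | 94.7% | 2.9% | 2.4% | 95.7% |

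**Where the misses come from, at 4% v 1%.** The true difference is 3 points. The chance of no admissions in the 4% arm is 0.96^50 = 0.130. Given that:

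- 0 v 0 has probability 0.130 × 0.99^50 = 0.130 × 0.605 = 0.079. The interval is 0 to 0.
- 0 v 1 has probability 0.130 × 50 × 0.01 × 0.99^49 = 0.130 × 0.306 = 0.040. SE = √(0.0196/49) = 0.020, so the upper limit is −0.020 + 1.984 × 0.020 = 0.020, below 0.03.
- 0 v 2 has probability 0.130 × 1225 × 0.0001 × 0.99^48 = 0.130 × 0.0756 = 0.010. SE = √(0.0384/49) = 0.028, so the upper limit is −0.040 + 1.984 × 0.028 = 0.016.

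Together these give about 0.128 of the 0.130 lying below the truth. The failure is an interval that collapses when the arm with the higher rate happens to have no admissions.

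**No admissions at all.** With 2% in both arms the chance is 0.98^100 = 13%; at 2% v 1% it is 22%. The t statistic is then 0/0. Newcombe still gives a result: the Wilson upper limit is 3.84/(50 + 3.84) = 0.071, so the interval is −7.1 to 7.1 points.

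**False positives.** With equal rates in both arms, the t-test rejects 0.2% of the time at a 1% rate, 1.3% at 2%, 3.9% at 4%, 4.8% at 10% and 5.0% at 30%. It reaches 5.7% only at a rate of 50%.

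**The case against.** Four objections have weight.

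- **The pairing is open.** The sentence can be read as t-tests for tablets and regression for admission. That reading is fair, and the documents do not exclude it. It changes the fault from an unsuitable method to an unassigned one, because the type of regression is still not stated. Section 4 allows for consulting hospital statisticians as needed, but that does not prespecify anything.
- **No t-based interval is promised.** This is true. The coverage figures assume that the admission difference would be reported with the interval that goes with the named test.
- **Rare admissions are an inference.** Eligibility for same-day discharge suggests few admissions, but section 5(f) lists broad reasons for admission and section 3 says patients may or may not be admitted. If rates are about 10% v 5% or higher, little is lost.
- **The t-test is not liberal.** A reader might infer from a result such as 4 v 0 admissions (t-test p = 0.042, Fisher p = 0.117) that the plan would declare effects on a handful of events. The documents and the arithmetic do not support that. The false-positive rate stays at or below about 5% for rates up to 30%. The uncorrected chi-square for the same table is 100 × (4 × 50)²/(4 × 96 × 50 × 50) = 4.17, p = 0.041, almost the t-test's value. The gap from Fisher mostly reflects Fisher's conservatism (size 0.7% at a 5% rate, 3.1% at 30%).

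**Conclusion.** The point holds as one about estimation and about an unassigned method, not about false positives. If the t-test is used for admission and admissions are rare, the nominal 95% interval covers between 77% and 93.5% over the assumed pairs from 2% v 1% to 10% v 2%. The error is mainly one-sided: at 4% v 1%, 13.0 of the 13.3 points of missed coverage lie below the true difference. It would be wrong to read the low coverage as overclaiming, since its usual effect is to understate a difference that exists. From 10% v 5% upward the loss is under 1 percentage point.

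The conclusion rests on assumed rates, on a two-sided 95% interval built from the pooled t-test, and on 50 analysed per arm. Admission is a secondary outcome, so the primary comparison is untouched. The change is worth making before the data are analysed, but the trial's validity does not depend on it.

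**What to change.** Replace the joint sentence in section 5(h) with one that assigns methods:

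- Limit the t-test to narcotic quantity.
- For admission, report the count in each arm and the risk difference with a Newcombe (score-based) 95% interval.
- Name one standard test for a 2x2 table, exact if counts are sparse.
- Name logistic regression, penalised if events are few, for any adjusted analysis.

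In the same edit, state whether the event is any admission or only admission for pain, since section 5(e) uses both. The choice also affects how rare the event will be.

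The cost is a sentence or two of text and no extra data. The Newcombe interval is wider and somewhat conservative at low rates: 19.5 points against 15.4 at 4 v 0, and 25.0 against 23.6 at 8 v 2. If Fisher's test is the one chosen, a borderline difference is less likely to be called significant.

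### The plan stops the trial on a significant difference, with looks at 50 and 100 patients, but sets no interim level or boundary; 0.05 at both looks gives an overall type I error of about 0.083

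*Combined protocol and SAP*

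**What the plan says.** Three consecutive items in section 5(i), the data-monitoring provisions, work together. Item 3, after covering adverse events, adds an efficacy assessment: "In addition the efficacy of the acupuncture in reducing pain will be determined". Item 4 sets the timing: "The data will be analyzed after 50 and 100 patients". Item 5 makes the stop mandatory: "The study will be terminated if it is determined that there is a significant difference between the study groups in post-operative pain control". Item 5 lists adverse events as a separate trigger.

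The primary outcome is set in section 5(e): "Primary outcome measures narcotic use at 24 hours". That section also states the aim: "The purpose of the present study is to determine the effectiveness of acupuncture in post-operative pain management in laparoscopic gynecological procedures". The tests are named in the analysis paragraph of section 5(h): "The analysis of pain medication use and admission rate will be performed using student t-tests and regression analyses".

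The only significance level appears in sections 5(c) and 5(h), in the sample-size text: "The Type I error probability associated with this test of this null hypothesis is 0.05". It belongs to a single test, which is to "reject the null hypothesis that the population means of the experimental and control groups are equal". Neither place mentions the look at 50 patients.

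**The concern.** Testing the same outcome twice, each time at the full level, and stopping on the first significant result gives chance two opportunities to produce a positive trial. The overall false-positive rate then exceeds the level of each test. Item 5 is worded as binding, and only the 50-patient look can shorten the trial, so that look can decide the primary conclusion.

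Two things are at stake. One is the type I error of the primary comparison, which was sized at 0.05 for one test. The other is the reported effect: a trial that stops early does so because its interim estimate was large, so the published difference is too big on average. The plan also leaves the stopping variable and its level open, so a reader of the results could not establish which error rate applied.

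**Working it through.** **Inputs from the document.** Level 0.05, difference 1.5 tablets, SD 2.4, power 0.8 and 47 per group (5(c) and 5(h)); 50 per group recruited (5(c)); looks at 50 and 100 patients (5(i) item 4); t-test (5(h)).

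**Assumptions not in the document.** The variable tested at both looks is 24-hour narcotic use. Tests are two-sided, as a null of equal means suggests. The first look has 25 per group and the last 50 per group. The outcome is normal.

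**The plan's own figure.** n per group = 2 × (1.960 + 0.842)² × 2.4² / 1.5² = 2 × 7.849 × 2.56 = 40.2, so 41, or 42 with the t distribution. The stated 47 is not reproduced. It would follow from 42 / 0.9 = 46.7 if 10% dropout had been allowed for, but no dropout rate is stated. The discrepancy is conservative and does not affect this point, because the two-look error depends only on the levels and the timing of the looks. A single t-test with 50 per group has power 0.872 for 1.5 tablets.

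**Overall type I error.** The test statistics Z1 (50 patients) and Z2 (100 patients) are approximately bivariate normal with correlation √(50/100) = 0.7071.

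Overall error = 1 − P(|Z1| < 1.96 and |Z2| < 1.96) = **0.0831**.

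Simulated t-tests gave 0.083 to 0.084. Relative to the sizing level: 0.0831 / 0.05 = 1.66.

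**How far the figure moves:**

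| Variation | Overall type I error |
|---|---|
| First 50 split 22/28, 20/30, 18/32 | 0.0834, 0.0838, 0.0844 |
| Skewed outcome (gamma, mean 3, SD 2.4) | 0.0815 |
| Final analysis at 94 patients | 0.0820 |
| One-sided 0.05 at both looks | 0.0801 |
| Interim 0.001, final 0.05 | 0.0502 |
| Interim 0.005, final 0.05 | 0.0519 |
| Interim 0.01, final 0.05 | 0.0546 |

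Only a stricter interim level changes the picture, and the plan states none.

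**If the true difference is 1.5 tablets.** The standard error at 25 per group is 2.4 × √(2/25) = 0.679. The smallest observed difference that stops the trial is 2.011 × 0.679 = 1.36 tablets at p < 0.05. The trial stops at 50 with probability 0.581. The expected size is 50 × 0.581 + 100 × 0.419 = about 71 patients. The mean estimate is 1.95 tablets among stopped trials (1.95 / 1.5 = 1.30, a 30% overstatement) and 1.63 over all trials.

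**A boundary that keeps 0.05.** O'Brien-Fleming with two equally spaced looks has constant 1.9774. The critical values are 1.9774 × √2 = 2.797 (p = 0.0052) at 50 patients and 1.977 (p = 0.0480) at 100. The overall error is 0.0500. For 1.5 tablets, power is 0.869, the probability of stopping at 50 is 0.251 and the expected size is about 87 patients. The mean estimate is 2.33 tablets among stopped trials and 1.60 over all trials.

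**The case against.** The strongest objection is that item 5 speaks of pain control, while the primary outcome is consistently called narcotic use or consumption. Section 5(f) uses adequacy of pain control as a discharge and admission criterion, and section 5(h) lists pain scale scores separately from medication taken. Suppose a pain score triggers the stop and narcotic use is tested once, at the stop or at 100. The type I error for narcotic use then depends on the correlation between the two, which the document does not give. It is 0.050 at correlation 0, 0.053 at 0.5 and 0.057 at 0.7, and reaches 0.083 only at correlation 1. This stands as far as it goes: 0.083 belongs to one reading. It does not rescue the plan, because the rule would then be undefined, and claiming success on either variable would raise the error further.

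Two lesser points are correct. The 0.083 counts false positives in both directions; in favour of acupuncture alone it is about 0.042, against 0.025 for a single two-sided test, which is the same ratio. And item 5 does not itself mention 50 patients. But item 4 gives only two looks, and only the first can end the trial early.

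The section heading refers to safety, but items 3 and 5 bring in efficacy explicitly. A strict interim level may have been intended, but it is not written, and it has to be fixed before the data are seen.

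**Conclusion.** The concern holds. The plan contains a binding efficacy stop with two analyses and no interim level, boundary or adjusted final level. On the most natural reading (24-hour narcotic use, two-sided 0.05 at both looks, equal groups), the overall type I error is about 0.083 instead of 0.05. That figure is stable, at 0.080 to 0.084, across sidedness, skewness, unequal splits and a slightly smaller final sample. It would fall to between 0.050 and 0.055 only with an unstated interim level of 0.01 or stricter. Under the plan's own effect and SD, an early stop is more likely than not, and the effect reported after one is about 30% too large on average. The omission itself is certain; 0.083 is conditional on the reading given. Because the rule governs the primary conclusion and cannot be credibly repaired after the 50-patient analysis, it must be settled before then.

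**What to change.** Reword items 3 to 5 of section 5(i) in one of two ways, leaving the adverse-event trigger in item 5 as it is.

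- **(a) Safety-only look at 50.** Remove the efficacy analysis and the efficacy stop at that look, and keep 0.05 for the single final test. Power for 1.5 tablets is 0.872, and the overestimate from early stopping disappears. The cost is that the trial always runs to 100 patients unless stopped for safety, against an average of about 71 under the present rule if the 1.5-tablet effect is real.
- **(b) A stated boundary.** Name 24-hour narcotic use as the only efficacy stopping variable and prespecify a boundary that keeps 0.05 overall. One example is O'Brien-Fleming: stop at 50 only if two-sided p < 0.0052, otherwise test at p < 0.048 at 100. Any other prespecified boundary that keeps 0.05 overall would also do. Power is 0.87, against about 0.886 under the present rule, whose higher figure comes with the inflated error. The chance of stopping at 50 falls from 0.58 to 0.25.

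Option (b) corrects the error rate but not the overestimate. Stopping would need an observed difference of about 1.99 tablets instead of 1.36, so the mean estimate among stopped trials rises from 1.95 to 2.33. Over all trials it barely changes (1.60 against 1.63).

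Neither option increases the planned 100 patients.
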